This document contains confidential information, which is the property of Smith & Nephew, Inc. Do not copy, disclose, or circulate without written authorization from the appropriate Smith & Nephew personnel

CONFIDENTIAL DOCUMENT
This document contains confidential information, which is the property of Smith & Nephew, Inc. Do not copy, disclose, or circulate without written authorization from the appropriate Smith & Nephew personnel.

5. Remove NPWT topical dressing to assess the target ulcer.
6. Assess level of pain, post NPWT dressing removal, using the VAS.
7. Complete reason for dressing change assessment and record any additional dressing changes since previous assessment as an unscheduled visit.
8. Assess target ulcer and record if target ulcer is closed or if target ulcer is ready for and will be surgically closed.

Note 1: If the target ulcer is closed, skip procedures 9-15 and complete procedure 16.

Note 2: If target ulcer is ready for and will be surgically closed, skip procedures 9-16 and complete procedure 17.

9. Examine the ulcer for evidence of infection, and treat the infection as appropriate per local protocol.
10. Debride the ulcer if indicated, at the discretion of the Investigator.
11. If the target ulcer remains open, photograph and determine the post-debridement ulcer area (cm²), perimeter (cm), greatest depth (mm), volume (cm³), and maximum linear dimension (cm) using the ARANZ Silhouette wound imaging and measurement device if applicable.

If debridement is not performed, an image of the target ulcer is still required to determine the ulcer area (cm²), perimeter (cm), greatest depth (mm), volume (cm³) and maximum linear dimension (cm) using the ARANZ Silhouette wound imaging and measurement device.

12. Conduct an ulcer assessment using the modified Bates-Jensen wound assessment tool and record percentage tissue type/condition of peri-wound skin assessment (Normal, Erythematous, Edematous, Eczematous, Excoriated, Macerated, Indurated).
13. Re-application of investigational product (PICO) or comparator tNPWT system

according to randomization schedule.

Record any additional dressings used and rationale for using this dressing.

Type of wound filler dressing if used (foam or gauze-based filler dressing).

Number of personnel used to apply NPWT system.

Time used to apply NPWT system (minutes).

Record level of negative pressure, intensity setting and delivery mode selected for tNPWT subjects, if appropriate for device selected.

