10. **Target ulcers open and ready for surgical closure only:**

- Conduct an ulcer assessment using the modified Bates-Jensen wound assessment tool and record percentage tissue type/condition of peri-wound skin assessment (Normal, Erythematous, Edematous, Eczematous, Excoriated, Macerated, Indurated).

11. Apply only the Profore compression bandage for VLU subjects whose target ulcer is closed.

Appropriate treatment for VLU subjects whose target ulcer will be surgically closed is left to the Investigator's discretion.

Appropriate treatment for DFU subjects is left to the Investigator's discretion.

12. Subjects to complete Cardiff Wound Impact Schedule (CWIS) quality of life questionnaire and EQ-5D.
13. Subjects will be instructed to refrain from using excluded medications and to return to the office for End of Treatment Assessment Visit 14 in 7 (\pm 1) days.

9.1.6 End of Treatment Assessment or Early Discontinuation Visit 14

1. Subjects will be queried regarding any changes in general health and the use of concomitant medications.
2. Any AE associated with the target ulcer and all SAE of any kind reported since the last assessment will be recorded in the appropriate eCRF. DevD will be recorded in a separate eCRF (see "Section 12, *Adverse Events*" for reporting and evaluating AE). Also, subjects will be queried as to any additional ulcer-related interventions requiring hospital admission, surgical intervention or specialist referral since the last assessment.

CONFIDENTIAL DOCUMENT
This document contains confidential information, which is the property of Smith & Nephew, Inc. Do not copy, disclose, or circulate without written authorization from the appropriate Smith & Nephew personnel

3. **For subjects whose target ulcer remained open during the treatment period, the following procedures should be completed:**
 - Assess level of pain from dressing wear, since the previous study visit, using the VAS.
 - Prior to examination of the ulcer, remove compression bandaging (**for VLU subjects**) and photograph the NPWT topical dressing using the ARANZ Silhouette wound imaging and measurement device.
 - Remove NPWT topical dressing to assess the target ulcer.
 - Assess level of pain, post NPWT dressing removal, using the VAS.
 - Subjects to complete Cardiff Wound Impact Schedule (CWIS) quality of life questionnaire and EQ-5D
4. Record any additional dressing changes since previous assessment as an unscheduled visit.

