17. STUDY PLAN

Table 17-1: Study Procedures by Treatment Plan

Parameter	Screening Run-in Period		Treatment Period Weekly Visits (±1 day)		End of Treatment Weekly Visits	
	Trial Visit Screen/Run- in Visit 1	Screen/Run- in Visit 2	Study Visit 1	Study Visits 2 to 12	Study Visit 13 ^c	Study Visit 14
Informed Consent	X					
Quality of Life Questionnaires (CWIS, EQ-5D)			X	X ^d	X ^d	X ^e
Register with sealed envelope (IWR)	X	X				
Demography	X					
Inclusion/Exclusion Criteria	X	X				
Medical Hx Including Ulcer Disease Hx	X					
Physical Exam including Vital Signs	X					
Selection of Target Ulcer	X					
VAS Pain Assessments	X	X	X	X	X	X ^e
Examine Target Ulcer for infection	X	X		X		
Photography and Measure Ulcer Size	X	X		X	X	X
Great Toe Pressure or ABI (or TcPO ₂)	X					
Blood collection for hematology, chemistry, pre-albumin and HbA _{1c}	X					
Urine Pregnancy Test	X ^a					X ^a
Randomization			X ^b			
Application of NPWT & Device questions			X	X		
Target ulcer & peri-wound assessment			X	X	X	X
Ulcer Care	X	X	X	X	X	
Subject Satisfaction Questionnaire						X
Assessment of Adverse Events or DevD	X		Assessed throughout the trial			
Concomitant Medications	X		Assessed throughout the trial			

a If subject is female of child-bearing potential, a pregnancy test is required.

b Subjects will be randomized only after the Investigator has verified that all inclusion/exclusion criteria are met.

c Subject's target ulcer judged to have not closed at Visit 13 will not complete the procedures for this Visit, but will complete the End of Treatment Assessment or Early Discontinuation Visit 14 procedures.

d Subjects to complete CWIS and EQ-5D only if the target ulcer is closed or will be surgically closed during the treatment period.

e Subjects to complete CWIS, EQ-5D and VAS assessments only if the target ulcer remained open during the treatment period.

CONFIDENTIAL DOCUMENT
This document contains confidential information, which is the property of Smith & Nephew, Inc. Do not copy, disclose, or circulate without written authorization from the appropriate Smith & Nephew personnel

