Duration of wear = Date of removal visit – Date of application visit – duration of study therapy interruption

If an unscheduled visit takes place between consecutive assessments multiple duration of wear values will be derived:

Duration of wear 1= Date of unscheduled visit – Date of application study visit

Duration of wear 2= Date of removal study visit – Date of unscheduled visit – duration of study therapy interruption

If more than one unscheduled visit occurs between consecutive assessments, further multiple wear times will be derived as above.

27. The average wear time per patient (patient level) will be derived as follows per subject:

Sum of duration of dressing wear (dressing level) values / Count of duration of dressing wear (dressing level) values

28. The median value for the baseline (Run-In Visit 2/Study Visit 1) target ulcer area will be derived for both the Full Analysis Set and Per Protocol populations by wound type and overall. The median value will also be derived for the depth and volume.

29. Whether or not the reference ulcer is clinically infected at any Study Visit.

30. Whether or not the reference ulcer has signs of infection at any Study Visit.

31. Whether an intervention was required will be derived for each subject:

If an unscheduled visit is recorded, where the reason for intervention is not given as routine: Intervention = Yes

If no unscheduled visits are recorded: Intervention = No

32. Whether prescription of an antibiotic was required will be derived for each subject:

If "have any systemic antibiotics been prescribed" = Yes at any assessment, or any antibiotic medications are recorded on the concomitant medications form, with a start date after randomization: Antibiotic = Yes

Document Number: 1004313

Document Version: 06

Document Part: 000

Document Status: Released

If "have any systemic antibiotics been prescribed" = No at all assessments, and no antibiotic medications are recorded on the concomitant medications form:
Antibiotic = No

33. Whether an intervention or prescription of an antibiotic was required will be derived for each subject:
If Intervention derivation (Derived Variable 31) = Yes or Antibiotic derivation (Derived Variable 32) = Yes, then need for intervention or antibiotic= Yes
If Intervention derivation (Derived Variable 31) = No or Antibiotic derivation (Derived Variable 32) = No, then need for intervention or antibiotic= No

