4.11 Exploratory Variables

Presence of Infection and Clinical signs of infection

A Fishers Exact test will be used to test for a difference in the percentage of subjects with incidence of infection presenting during the 12-week treatment period between treatments using the Full Analysis Set, the corresponding 95% confidence intervals will also be presented.

The presence of infection and clinical signs of infection will be summarized by regular Study Visit, at treatment discontinuation and, where appropriate at the one-week confirmation visit. Whether the reference wound is clinically infected at any post baseline assessment will also be summarised.

In addition, the summaries will be separated by reference wound filler used at baseline (gauze, foam or none).

Whether the reference wound has signs of clinical infection at any post baseline assessment and whether the reference wound has signs of clinical infection at treatment discontinuation will be cross tabulated against whether the reference wound has signs of clinical infection at baseline separately for each treatment.

Need for administration of antibiotics and additional interventions

A Fishers Exact test will be used to test for a difference in the percentage of subjects requiring either the administration of antibiotics or additional interventions, between treatments using the Full Analysis Set. The corresponding 95% confidence intervals will also be presented. Individually, Fishers Exact tests will be used to test for a difference in the percentage of subjects requiring the administration of antibiotics and additional interventions separately, between treatments.

The need for administration of antibiotics and additional interventions (and either intervention), and type of intervention will be summarized at per subject by treatment and wound type.

Dressing wear time

A linear regression model will be fitted to the average wear time per subject. Treatment, center, wound type, baseline ulcer area, baseline exudate level and baseline mobility level will be included in the initial model. The difference between the two treatments in terms of average wear time per subject (treatment parameter estimate) will be presented along with the 95% confidence intervals.

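### The scheduled infection examination ends at Study Visit 12, yet the SAP analyses infection at treatment discontinuation and over the full 12 weeks

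*SAP*

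**What the plan says.** **What the SAP analyses.** Section 4.11 has infection and its clinical signs "summarized by regular Study Visit, at treatment discontinuation and, where appropriate at the one-week confirmation visit". It adds that "whether the reference wound has signs of clinical infection at treatment discontinuation will be cross tabulated" against baseline signs, separately by treatment. It also applies Fisher's exact test to "incidence of infection presenting during the 12-week treatment period between treatments". The per-subject variable is SAP 4.3 item 29: "Whether or not the reference ulcer is clinically infected at any Study Visit". Item 30 does the same for signs of infection.

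**What the protocol collects.** In 9.1.4 (Visits 2-12) the examination is step 9: "Examine the ulcer for evidence of infection, and treat the infection as appropriate per local protocol". The row "Examine Target Ulcer for infection" in Table 17-1, in both protocol and SAP, is marked at Run-in Visits 1 and 2 and Study Visits 2-12, and is blank at Visits 13 and 14. (It is also blank at Study Visit 1, which is harmless because that visit falls on the same day as Run-in Visit 2.) Step 8, Note 2 says: "If target ulcer is ready for and will be surgically closed, skip procedures 9-16 and complete procedure 17". Step 17 lists imaging, the modified Bates-Jensen tool with the peri-wound scale, and questionnaires, but no infection examination. The lists for Visit 13 (9.1.5) and Visit 14/Early Discontinuation (9.1.6) have none either.

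**How gaps are filled.** SAP 2.3.5 sets infection and signs to No for ulcers recorded as closed. Other values needed at the end of the 12 weeks are carried forward from the last non-missing post-baseline visit.

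**The concern.** The SAP specifies tables for a time point at which the protocol schedules no measurement. Photography and peri-wound assessment are marked at Visits 13 and 14 in the same tables, so the infection row is a specific omission and not a general thinning of the last visits.

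Incidence of target ulcer infection is a listed exploratory objective. A value carried forward into the discontinuation table would look observed when it is not. The trial is open-label, so reasons for stopping could differ by arm; if they do, unobserved status at stopping could distort the comparison. An examination not made at the visit cannot be recovered later.

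**Working it through.** No plan figure has to be reproduced. The check sets the procedure lists beside the SAP's time points.

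| Situation | List that applies | Infection examination | What the SAP would use |
|---|---|---|---|
| Open at Visits 2-12, continuing | 9.1.4 steps 1-15 | Yes, step 9 | Observed |
| Closed at Visits 2-12 | 9.1.4 step 16 | No | Imputed No |
| To be surgically closed, Visits 2-12 | 9.1.4 step 17 | No | Still open when assessed, so the closed-ulcer rule does not clearly apply; missing or carried forward |
| To be surgically closed, Visit 13 | 9.1.5 | No | As above |
| Open at Visit 13 | Sent to 9.1.6 | No | Missing or carried forward, at best from Visit 12 |
| Early discontinuation, ulcer open | 9.1.6 (through 9.2) | No | Missing or carried forward |
| Re-opened at Visit 14 | 9.1.6 | No | Missing or carried forward |

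**Timing.** SAP 4.3 item 7 puts Visit 2 at day 7 and Visit 3 at day 14, so Visit k falls on day 7 × (k − 1). Visit 12 is day 7 × 11 = 77 and Visit 13 is day 7 × 12 = 84, each ±1 day. For an ulcer that stays open, 11 of 12 wear weeks end with a scheduled infection examination. The unexamined share is 1/12 = 8.3%.

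**Illustrative size, completers with open ulcers.** The documents give no infection rate. Assume a constant weekly hazard of 1.5%:
- Through 12 weeks: 1 − (1 − 0.015)^12 = 16.6%.
- Through 11 weeks: 1 − (1 − 0.015)^11 = 15.3%.
- Difference: 0.015 × (1 − 0.015)^11 = 1.3 percentage points.
- Halving the assumed hazard to 0.75% gives 0.0075 × 0.9925^11 = 0.7 points. Doubling it to 3% gives 0.03 × 0.97^11 = 2.1 points.
- With 80 per arm, 80 × 0.013 is about 1 subject per arm. That is a ceiling at the 1.5% hazard, because it assumes every ulcer stays open for 12 weeks and nothing else catches the event.

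**Early stoppers.** The planned 20% drop-out is 0.20 × 160 = 32 subjects. At the same hazard, one unexamined week each gives 32 × 0.015 = about 0.5 events. Not all 32 are affected: some may never attend Visit 14, and some may stop at a weekly visit where step 9 was done.

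**The case against.** **Other capture exists.** At Visit 14, open and re-opened ulcers are scored on the modified Bates-Jensen tool, whose categories include purulent exudate and bright red surrounding skin. They are also scored on a peri-wound scale that includes erythema, edema and induration. Step 17 and Visit 13 step 10 do the same for ulcers going to surgical closure. Of the five signs in the synopsis (redness, swelling, tenderness, heat, purulence), only tenderness and heat have no counterpart. Target-ulcer adverse events are queried at Visits 13 and 14, antibiotics are recorded, and interim dressing changes are logged as unscheduled visits. This stands: a reader might infer that the last week of wear escapes all scrutiny, and it does not. But the investigator's judgement on infection is not scheduled there, and the SAP does not derive items 29-30 from these sources.

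**The confirmation visit is largely covered.** The SAP qualifies it as where appropriate and imputes No for closed ulcers. This also stands, leaving re-opened ulcers.

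**Subjects stopped for infection are not the ones lost.** A reader might infer that they are, because non-responding infection is a mandatory reason to stop treatment in 9.2. That rule needs two weeks of failed therapy, so the infection would usually have been found earlier under step 9 and item 29 would already be Yes. For them the loss is mainly status at discontinuation.

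**The number missed is unknown.** A reader might infer a large loss among early stoppers: if 20-40% of the 32 had a first infection in their last interval, 6-13 events would be missing. No document supports such a fraction, and it is 13 to 27 times the 1.5% weekly rate assumed above.

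**General wording.** Protocol 9.4 says the investigator assesses the ulcer at each visit and also assesses infection. It ties infection to no visit and does not override the schedule.

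**Conclusion.** The mismatch holds and rests only on the documents' own schedules. SAP 4.11 calls for infection status at treatment discontinuation and incidence over 12 weeks. For ulcers open at discontinuation or at week 12, re-opened at Visit 14 or awaiting surgical closure, the protocol schedules no examination that would supply it.

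The consequence is modest. The endpoint is exploratory, and no primary, key secondary or other secondary conclusion depends on it. A reader might take infection to be the trial's main wound-safety outcome, but the documents define safety as recording target-ulcer adverse events and all serious adverse events. The 1.3-point shortfall in completers depends on the assumed 1.5% hazard and on no other capture. Bias between arms is possible only if stopping, or infection at stopping, differs by arm, and nothing in the documents shows that it will. The CRF was not available; if it already has an infection page at these visits, the gap is one of protocol wording. The correction is still worth making, because it is cheap and the data cannot be collected afterwards.

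**What to change.** - Add the existing infection assessment (presence of infection and the listed clinical signs) to 9.1.6 for any ulcer that is open or re-opened at Visit 14/Early Discontinuation.
- Add it to 9.1.4 step 17 and to 9.1.5 for ulcers going to surgical closure. Closed ulcers at Visit 13 need no addition, since they skip step 9 by design at earlier visits.
- Mark these visits, with the open-ulcer condition, in Table 17-1 of both protocol and SAP.
- State in SAP 4.3 items 29-30 that these visits count towards the flags.

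This changes data collection only and no treatment rule. At these visits the ulcer is already uncovered where a dressing is on (the instruction "Remove NPWT topical dressing to assess the target ulcer" recurs in 9.1.5 and 9.1.6), it is photographed, and if open it is scored. The cost is about a minute per visit, a small CRF change, and wording edits to the two documents.

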9.1.4 Study Visits 2-12

The treatment period is defined as Randomization Study Visit 1 through Study Visit 12. During the study treatment period, any AE associated with the target ulcer and all SAE of any kind will be recorded in the appropriate eCRF. Device deficiencies (DevD) will be recorded in a separate eCRF. The evaluation of all AE is described in Section 12, *Adverse Events*. All weekly visits

must be performed according to the study visit schedule (Section 17), preferably on the same day each week, to conduct all assessments and to assure compliance with treatment. A plus or minus one day visit window will be used for all study visits.

VLU subjects found to have target ulcer closure should continue the compression dressing. Appropriate treatment for DFU subjects found to have target ulcer closure is left to the Investigator's discretion. Appropriate treatment for VLU and DFU subjects, whose target ulcer is ready for and will be surgically closed, is left to the Investigator's discretion. If the Investigator believes the target ulcer is ready for surgical closure, then this procedure should be completed within the same week of the scheduled study visit. The next scheduled visit for subjects with closed target ulcers or subjects that will be surgically closed will be designated as End of Treatment Assessment Visit 14 and should occur in 7 (± 1) days.

All study procedures should occur in the order outlined in the protocol. Study Visits occurring outside the protocol specified visit window should be completed and recorded as a protocol deviation.

1. Subjects will be queried regarding any changes in general health and the use of concomitant medications.
2. Any AE associated with the target ulcer and all SAE of any kind reported since the last assessment will be recorded in the appropriate eCRF. DevD will be recorded in a separate eCRF (see "Section 12, *Adverse Events*" for reporting and evaluating AE). Also, subjects will be queried as to any additional ulcer-related interventions requiring hospital admission, surgical intervention or specialist referral since the last assessment.
3. Assess level of pain from NPWT dressing wear, since the previous study visit, using the VAS.
4. Prior to examination of the ulcer, remove compression bandaging (**for VLU subjects**) and photograph the NPWT topical dressing using the ARANZ Silhouette wound imaging and measurement device.

CONFIDENTIAL DOCUMENT

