The standardised residuals will be assessed for normality (histograms, quantile-quantile plots), homoscedacity (plots against regressors) and no large outliers (magnitude, covariance ratio, DFBETAS). Should these assumptions not hold or if N<20 then non-parametric bootstrapping may be applied to generate 95% confidence intervals of the model estimates. If these differ widely from those of the linear regression model then the bootstrapping estimates will be used these will be used.

The average wear time per subject (at a subject level) will be summarized by treatment, wound type, and the remaining covariates detailed in the previous paragraph. The duration of dressing wear (at a dressing level) will also be summarized by treatment, center, wound type, level of mobility at baseline, level of exudate at the previous assessment and ulcer area (categorized) at the previous assessment.

ST:

9 7 5

Reference:

CE/052/PIC

Customer Code:

0 5

Impact of the device on aspects of daily living and satisfaction with device therapy

All response questions to the exit survey will be summarized by treatment, center, wound type and baseline level of mobility.

A Cochran-Mantel-Haenszel will be used to test for a difference between treatments in individual responses to the Exit Survey for: Overall satisfaction, Opinion of using the device on another wound in future, comfortable to wear, activity level change, and the use of the NPWT device was disruptive to my sleep.

Pain on removal of dressing, at initiation of therapy and during wear

The level of pain on initiation of therapy will be summarized by Study Visit and treatment, separately for each wound type and overall.

The level of pain on initiation of therapy will also be summarized for the ActiV.A.C.® treatment arm overall Study Visits by whether intermittent or continuous therapy is applied, and by pressure range applied (for intermittent – the high therapy pressure value will be used), and compression rate, at the current Study Visit.

The level of pain during wear, and on removal, will be summarized by Study Visit and treatment, separately for each wound type and overall.

The level of pain during wear, and on removal, will also be summarized for the ActiV.A.C.® treatment arm overall Study Visits by whether intermittent or continuous therapy is applied, and by pressure range applied (for intermittent – the high therapy pressure value will be used), and compression rate, at the current Study Visit.

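### SAP 4.11 groups comparator-arm wear and removal pain by the device setting recorded after that pain was scored, so the pairing is off by one visit

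*SAP*

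**What the plan says.** SAP 4.11, in the part on pain, plans two breakdowns for the comparator arm. The first groups pain on initiation of therapy by mode (intermittent or continuous), pressure range and compression rate at the current visit. The second applies the same grouping to the other two scores: "The level of pain during wear, and on removal, will also be summarized for the ActiV.A.C.® treatment arm overall Study Visits", again by mode, pressure range and "compression rate, at the current Study Visit".

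Protocol 9.1.4 sets the sequence for Study Visits 2-12 and adds that "All study procedures should occur in the order outlined in the protocol". The relevant steps are:

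- Step 3: "Assess level of pain from NPWT dressing wear, since the previous study visit, using the VAS".
- Step 6, after the old dressing is off: "Assess level of pain, post NPWT dressing removal, using the VAS".
- Step 13, at re-application: "Record level of negative pressure, intensity setting and delivery mode selected for tNPWT subjects, if appropriate for device selected".
- Step 14: pain during initiation of therapy.

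The synopsis leaves pressure, intensity and delivery mode to the investigator at each treatment visit, so settings may change from week to week.

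**The concern.** Wear pain looks back over the interval since the last visit, and removal pain concerns the dressing just taken off. The setting recorded at the same visit belongs to the next dressing, which has not been applied when either score is taken. Read literally, the SAP groups a pain score by a setting that came after it.

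If an investigator changes the setting because of the pain just reported, the table credits the new setting with the pain that prompted the change. What is at stake is the only planned tabulation of wear and removal pain against the comparator's delivered pressure and mode.

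**Working it through.** The plan gives no figure for this table, so there is none to reproduce. The check has two parts.

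**1. Tracing the visits**

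| Score | Dressing concerned | Setting in force was recorded at | SAP groups by |
|---|---|---|---|
| Wear pain, visit n (step 3) | in place since visit n-1 | visit n-1 | visit n |
| Removal pain, visit n (step 6) | just removed | visit n-1, or a mid-week change | visit n |
| Initiation pain, visit n (step 14) | just applied | visit n | visit n |

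Only the last row matches. Visits are 7 (±1) days apart, so the mismatch is about one week.

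A subject treated for the full course has 12 wear intervals, scored at Study Visit 2 through Study Visit 13 or 14. The SAP rule can pair at most 11 of them (Visits 2-12), each with the following week's setting. The cases at the ends are:

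- The Study Visit 1 setting governs the first interval but is never paired with wear or removal pain.
- Wear and removal pain are scored at Study Visit 13 (closed or for surgical closure, protocol 9.1.5) or Study Visit 14 (still open, 9.1.6). SAP 2.2 and Table 17-1 show no NPWT application at those visits.
- At a closure or surgical-closure visit within Visits 2-12, steps 3 and 6 are done but Notes 1 and 2 under step 8 skip step 13. Those scores have no current setting either.

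**2. What the mismatch can do**

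A hand example with assumed values: five subjects at 150 mmHg score 60 mm and are lowered to 75; five at 100 mmHg score 30 mm and are raised to 125. Call 125 or more high.

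- By the setting in force: 60 - 30 = +30 mm (high minus low).
- By the setting chosen afterwards: 30 - 60 = -30 mm.

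A simulation shows how far this depends on the pattern of changes. All its pain inputs are assumptions: 80 comparator subjects, Visits 2-12, 40 replicates, residual SD 12 mm, starting settings 75-150 mmHg, settings kept within 40-200 mmHg. Pain at each visit is generated from the previous visit's setting with a true slope of 0.2 mm per mmHg, first with no between-subject variation.

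| How settings change | Slope by previous visit's setting | Slope by current visit's setting |
|---|---|---|
| Never | 0.199 | 0.199 |
| At random, about 37% of visits | 0.197 | 0.099 |
| Lowered by 25 mmHg if pain >40 mm | 0.196 | 0.100 |
| Lowered as above, and raised by 25 mmHg if pain <20 mm | 0.199 | -0.106 |

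In the last row the sign was reversed in every replicate.

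Next, let subjects differ in their general pain level:

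| Rule | Between-subject SD | Previous visit's setting | Current visit's setting |
|---|---|---|---|
| Lowered and raised | 8 mm | 0.054 | -0.097 |
| Lowered and raised | 15 mm | -0.046 | -0.132 |
| Lowered only | 8 mm | 0.096 | 0.006 |
| Lowered only | 15 mm | -0.038 | -0.119 |

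The current-visit table is further from 0.2 in every row, but the previous-visit table is not unbiased either.

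**The case against.** The strongest reply is that the consequence is small and conditional. Much of it stands.

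- **How often settings change drives the result.** Take two settings, lowered above 40 mm and raised below 25 mm at every visit, with noise SD 15 mm, mean pain 32 mm and no between-subject variation. A true +10 mm then appears as about -22 mm. If the rule is followed only 30%, 10% or 5% of the time, the table shows about +0.4, +6.9 or +8.3 mm. The documents say nothing on how often settings change. A reader might infer that lower settings must look more painful whatever the truth; the documents do not support that.
- **The previous-visit pairing is not a cure.** Under the same every-visit rule with between-subject SD 12 mm, it gives about -1.5 mm for a true +10 mm and about -12.4 mm for no effect. A reader might take the corrected table as an estimate of the effect of pressure. It is not one, because settings may be chosen in response to pain.
- **It is not the plan's only look at setting and pain.** A reader might infer that it is, but SAP 4.11 also groups initiation pain by setting, correctly.
- **Mid-week changes.** Protocol 9.1.7 has tNPWT dressings changed 2-3 days after application, as an unscheduled visit, and does not require the setting to be recorded then. The dressing removed at a study visit may be one applied mid-week.
- **The wording might mean something else.** SAP 4.3 (item 40) describes interruption of therapy at each visit, and SAP 4.12 describes it as between visits. The case report form is not among the documents and might also capture the setting found on arrival. However, the protocol records the setting only at application, and the SAP uses the same phrase for initiation pain, where it must mean the setting just applied. SAP 4.11 also shows that an earlier value can be specified: dressing wear is split by exudate and ulcer area at the previous assessment.

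None of this makes the current wording right for wear and removal pain.

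**Conclusion.** The point holds as a misaligned grouping rule. It follows from the order of procedures and needs no assumption beyond reading the current visit's setting as the one recorded at step 13. Compression rate is not named in that step; I assume it is recorded together with the other settings.

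The direction and size of the distortion are conditional: none if settings do not change; attenuation if they change at random or, with no between-subject variation, are only lowered; possible sign reversal if they are both lowered and raised in response to pain. The millimetre and slope figures illustrate this under assumed inputs and do not predict what this trial would show.

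The severity is minor. The table is exploratory, descriptive and confined to one arm. A reader might infer that the PICO versus comparator pain results are at risk; they are not, because those summaries are by visit and treatment and do not use the setting. The primary analysis is also unaffected.

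**What to change.** In SAP 4.11, for pain during wear and on removal only, replace the reference to the current visit with: *recorded at the previous Study Visit (or at the most recent unscheduled re-application, where a setting was recorded)*. State that this includes scores taken at Study Visit 13 or 14 and at closure or surgical-closure visits. Keep the current-visit setting for pain on initiation. If the case report form captures the setting found on arrival and that was meant, say so instead.

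Add a line that the table is descriptive, because settings are at the investigator's discretion and the association can still be confounded by a subject's pain level.

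The cost is a short SAP edit and a merge on the previous visit in the table program. Settings from scheduled visits are already collected under the protocol. Settings at unscheduled changes can be used only where they were recorded, so their availability should be checked against the case report form.
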